We followed the USPSTF recommendation for the prevention of postpartum depression (2) by targeting pregnant women with moderate depressive symptoms, who could reasonably be considered as signaling distress or early signs of illness, are at high risk for postpartum depression, and are not eligible for specialized psychiatric care. Our program is a virtual and population-based preventive intervention, not a treatment for clinical depression, although it could reasonably be conceived as an adjuvant to psychiatric care.

Pregnant women inclusion criteria: Pregnant women (12-25 weeks' gestation), ages 14 years or older, with: 1) subclinical levels of depression (EPDS scores 9-12) and 2) ability to read and understand French.

Pregnant women exclusion criteria: 1) EPDS score in the clinical range (≥ 13) or no symptoms (EPDS < 9); 2) Positive screening of psychotic symptoms using the Psychosis Screening Questionnaire (PSQ); 3) self-reported substance abuse problems. These criteria are consistent with those of other prevention trials (51).

Partners inclusion criteria: 1) The spouse or any other significant person who will accompany the pregnant woman during pregnancy and after childbirth, chosen by the pregnant woman. 2) The pregnant woman has consented to participate in the study.

Participant allocation. Randomization will be centrally controlled by the CHU Ste-Justine Applied Clinical Research Unit (URCA), headed by co-PI [name]. An independent biostatistician will create the randomization scheme, a computer-generated random listing using a 1:1 allocation, according to trial statistician instructions. Random permuted blocks randomization will be used. The randomization list will be WEB-based and completed via REDCap.

Bias protection. With detailed informed consent procedures, it is expected that pregnant women will accept their randomized group allocation. The intervention team will be blinded to the initial level of depressive symptoms. No formal virtual depression prevention intervention program yet exists in Quebec. There will be no interference with usual medical/nursing care, which may include antidepressant medication and/or psychotherapy.

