Primary outcome. Maternal depression at 3 months' postpartum was chosen as the primary outcome to: 1) ensure comparability to other perinatal trials (60-67) and 2) to reduce potential biases induced by attrition. The primary outcome will be the proportion of women with EPDS scores above the clinical cut-off for depression (EPDS \geq 13)). Differences between experimental and control groups will be analyzed at T₁ (3 months' postpartum) and again at T₂ (6 months' postpartum, secondary outcomes). The EPDS is an internationally recommended 10-item self-report scale that assesses depressive symptoms on a 4-point scale; scores range from 0 to 30 with higher scores representing higher symptomatology. More than 80% of perinatal depression studies use self-report measures (73) and the majority use the EPDS. The EPDS was created to counter the limitations of other well-established depression scales when used during the perinatal period. It has been validated by standardized psychiatric interviews with large sample sizes and has well-documented reliability and validity of over 11 languages (50, 74). Participants will fill out the EPDS at 3 assessment times: baseline (T₀, as part of inclusion criterion), T₁, and T₂.

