Secondary outcomes. Participant and partner assessments at baseline, T₁ and T₂. The proposed intervention is based on CBT principles used to treat both anxiety and depression. As anxiety is highly correlated with perinatal depression, it is an important secondary outcome. **Generalized anxiety.** The proposed intervention is based on CBT principles used to treat both anxiety and depression. As anxiety is highly correlated with perinatal depression, it is an important secondary outcome. Anxiety will be assessed at all 3 time points, using the Generalized Anxiety Disorder 7-item (GAD-7) scale, an extensively validated self-report instrument (75-77). **Anxiety related to pregnancy** will be measured with the 10-item Pregnancy-specific anxiety scale (PRAQ-R2) (78, 79) at baseline. **Stress** will be assessed using the 10-item form of the Perceived Stress Scale, at six months postpartum (80, 81). **Well Being** will be evaluated with the 5-item WHO-5 well-being index at T₁ (82). **Self-efficacy** will be assessed using the 10-item General Self-Efficacy Scale (GSE) at 3 months postpartum (83, 84). **Self-Compassion** will be measured with the 12-item shortened version of the Self-Compassion Scale (SCS) (85-87), at 3 months postpartum. **Sleep.** Sleep may improve as a result of the increased capacity for relaxation, mindfulness, and emotional regulation fostered by the intervention. At 3 months postpartum, we will assess sleep quality, a critical aspect of perinatal maternal health, using the 19-item Pittsburgh Sleep Quality Index (PSQI) (88, 89), a self-report over a one-month interval with very good psychometric properties and validated for use during postpartum (90). **Tobacco, alcohol and drug use** will be self-reported at baseline and 3 months postpartum. **Social Adjustment** will be assessed using the 14-item screener version of the Social Adjustment Scale – Self-report (SAS-SR) (91, 92). Six major areas are covered: work (paid or unpaid), social and leisure activities, relationships with extended family, role as marital partner, role as a parent, and role within the family unit (including perceptions about economic functioning). For this study, we will only use the work subscale at 3 months postpartum. **Marital satisfaction** will be evaluated with the short version of the Dyadic Adjustment Scale (DAS-7) (93-95) at 3 months postpartum. **Co-parenting.** The proposed intervention is partner-inclusive and, as such, may improve co-parenting quality (the extent to which parents work together and agree on childcare and education). We will use a brief 14-item version of the Coparenting Relationship Scale (75) (e.g., partner pays a great deal of attention to our child; partner appreciates how hard I work at being a good parent) at 3 months postpartum. **Social Support** will be assessed at 6 months postpartum using the 10-item Social Provisions Scale (SPS-10) on emotional

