Economic evaluation. Service utilization will be measured using a slightly modified version of the **Health Service Utilization and Cost of Care Questionnaire** (105) to assess childcare expenses and travel costs incurred by patients to obtain care. Costs of administering the intervention include a) recruiting and training of nurses, b) nurses' time to provide the intervention, and c) supervision of nurses.

Planned Analyses

Data will be analyzed using SAS software using an intent-to-treat approach. A two-sided significance level of 0.05 will be used for the primary outcome; a significance level of 0.01 (two-sided) will be used for secondary and other outcomes to account for multiple outcomes. Demographic and other baseline variables will be compared between study groups using descriptive statistics (mean, standard deviation, proportions).

For the primary outcome, a two-sample sided test of proportion (chi-square test) will be used to compare the difference in the proportion of women with EPDS in the clinical range (> 13) at 3 months' postpartum. The same approach will be used for the 6-month assessment (secondary outcome). These analyses will be supplemented by an analysis using EPDS scores, where the baseline EPDS score will be used as covariate in an ANCOVA model including the 3- and 6-month EPDS scores. With this model, we will obtain 95% confidence intervals of EPDS score differences between intervention arms at 3 and 6 months' postpartum. Sensitivity analyses will be performed to investigate the potential bias introduced

by attrition. A method based on inverse-probability-of-attrition weights (IPAWs) will be used (101, 102).

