For secondary outcomes, the statistical method for comparing intervention arms will depend on the distribution of the outcome variable. For binary variables, chi-square tests will be used. The corresponding 95% CI for the difference in proportions will also be provided. In the unlikely event that randomized intervention arms are unbalanced for baseline variables known to be associated with primary and secondary outcomes, logistic regression will be used where unbalanced variables will be included. For continuous variables, we will use ANCOVA models as described above. Again, unbalanced variables will be added if needed. If the intervention is found to be effective, exploratory analyses will be conducted to explore the potential effect of moderator variables using causal inference models including gender and intervention compliance (103, 104). No formal interim efficacy analysis is planned. Ethical practices and conduct of the trial as well as all safety concerns will be reported to an independent Data and Safety Monitoring Committee.

Planned subgroup analyses. The ANCOVA models presented above will be expanded to include the socioeconomic status of the participant, ethnicity, personality disorder symptoms subgroup variable as well as interaction with the intervention.

Pilot Study

We conducted a feasibility study to assess acceptability and compliance to the intervention (n = 17). Pilot data indicate that women used a mix of electronic devices to access the intervention. All used an iPad at some time, 40% also used their smartphone and 20% also used a computer. Telephone follow-up by a nurse was rated as “essential” (40%), “very useful” (40%), or “useful” (20%). Online sessions were rated as “very useful” (60%) or “useful” (40%). Strategies proposed in the intervention (cognitive restructuring, relaxation, behavioral modification, social support) were used “regularly” (30%), “often” (50%), “occasionally” (10%), or “never” (10%). The material was rated as “very easy to understand” (90%) or “easy” (10%). Each strategy was used at least occasionally by 86% of women. Qualitative data indicated high levels of appreciation (Appendix A).

Ethical considerations

Voluntary informed consent

The recruiting process will allow women to give a voluntary informed consent (Appendix E). The consent form will be signed on the online platform provided by the URCA.

Confidentiality and Privacy Protection

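### The only covariate prespecified for the supplementary EPDS-score ANCOVA is the eligibility EPDS, confined to 9-12; it probably explains about 1-4% of variance, and less restricted T0 measures are not prespecified

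*Combined protocol and SAP*

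**What the plan says.** Planned Analyses makes a chi-square test on the proportion of women in the clinical EPDS range the primary comparison. It adds a supplementary model of the scores themselves, at 3 and 6 months: "the baseline EPDS score will be used as covariate in an ANCOVA model". No other covariate is named for that model.

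The Primary outcome paragraph gives the EPDS assessment times as "baseline (T₀, as part of inclusion criterion), T₁, and T₂", so the covariate is the screening score. The inclusion criteria require "subclinical levels of depression (EPDS scores 9-12", and the exclusion criteria remove women with "EPDS score in the clinical range (≥ 13) or no symptoms (EPDS < 9". On the full scale, "scores range from 0 to 30 with higher scores representing higher symptomatology".

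Under Secondary outcomes, GAD-7 is taken at all three time points. Pregnancy-specific anxiety "will be measured with the 10-item Pregnancy-specific anxiety scale (PRAQ-R2) (78, 79) at baseline". For the other continuous outcomes, Planned Analyses says: "For continuous variables, we will use ANCOVA models as described above". It then allows baseline variables to be added if the arms prove unbalanced on them.

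Pregnant Women Recruitment has eligible women randomised through REDCap and told their arm after the eligibility call. The baseline questionnaire is described later, under Partners Recruitment, as sent to women already recruited; completing it opens access to the website.

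**The concern.** Baseline adjustment narrows the confidence interval only as far as the covariate predicts the outcome among the women randomised. A baseline EPDS normally predicts a later EPDS well, but here eligibility removes nearly all of its spread. The plan therefore carries an adjustment that looks useful and probably does little.

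T0 GAD-7 and PRAQ-R2 are not eligibility criteria, and the protocol itself describes anxiety as strongly related to perinatal depression. Neither is named in advance as a covariate. At stake is precision in the supplementary EPDS-score analysis and, where an outcome has its own T0 value, in the continuous secondary outcomes, which are tested at two-sided 0.01.

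**Working it through.** **The plan's own figure.** Inputs from the Sample size paragraph: 20% v 10%, 80% power, two-sided 5%.

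n per arm = [1.96·√(2·0.15·0.85) + 0.842·√(0.2·0.8 + 0.1·0.9)]² / 0.10² = 199.

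Attrition of 20% gives 199/0.80 = 249 per arm (498 in total). Two successive losses of 10% give 199/0.81 = 246 (492). The stated 500 is reproduced, and it uses no covariate. The analysable number at 3 months is 250 × 0.9 = 225 per arm.

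**Screening EPDS alone.** If 9, 10, 11 and 12 are equally likely, SD = √1.25 = 1.118. The documents do not give the unrestricted EPDS SD or the pregnancy-to-postpartum correlation r. I assume SD 4-6 and r 0.4-0.6. With u = 1.118/SD, the correlation after restriction is r′ = r·u / √(1 − r² + r²u²). The equivalent number of extra women per arm is 225/(1 − R²) − 225.

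| Assumed SD | r | r′ | R² | Extra women per arm |
|---|---|---|---|---|
| 6 | 0.4 | 0.081 | 0.7% | 1.5 |
| 5 | 0.5 | 0.128 | 1.6% | 3.7 |
| 4 | 0.6 | 0.205 | 4.2% | 9.9 |

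Unrestricted, these correlations would give R² of 16-36%. Widening r to 0.3-0.7 gives a restricted R² of 0.3-7.0%.

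**Adding T0 GAD-7.** Selecting on EPDS also shrinks GAD-7. With E the screening EPDS, G the T0 GAD-7 and Y the later EPDS, all standardised before selection, each covariance becomes ρ(a,b) − ρ(a,E)·ρ(b,E)·(1 − u²).

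Mid case, all assumed: SD 5, ρ(E,Y) 0.5, ρ(E,G) 0.6, ρ(G,Y) 0.45. Then u² = 0.05, and:
- var E = 0.05; var G = 1 − 0.36·0.95 = 0.658; var Y = 1 − 0.25·0.95 = 0.7625.
- cov(E,G) = 0.030; cov(E,Y) = 0.025; cov(G,Y) = 0.45 − 0.30·0.95 = 0.165.
- EPDS alone: R² = 0.025²/(0.05·0.7625) = 1.6%.
- Given EPDS, var G = 0.658 − 0.018 = 0.640 and cov(G,Y) = 0.165 − 0.015 = 0.150. GAD-7 adds 0.150²/(0.640·0.7625) = 4.6 points, for a total of 6.25%.
- Gain over EPDS alone: 225/0.9375 − 225/0.9836 = 240.0 − 228.75 = about 11 women per arm. The interval is narrower by 1 − √(0.9375/0.9836) = 2.4%.

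Over SD 4-6, ρ(E,Y) 0.4-0.6, ρ(E,G) 0.5-0.7 and ρ(G,Y) 0.4-0.5:
- Lowest: 4.2% rises to 4.3% (SD 4; 0.6, 0.7, 0.4), worth 0.3 women per arm.
- Highest: 0.7% rises to 14.8% (SD 6; 0.4, 0.5, 0.5), 14 points and worth about 38 women per arm.

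The SD of GAD-7 falls to 0.73-0.88 of its unrestricted value over this grid. What PRAQ-R2 would add on top was not calculated.

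**In terms of the 0.01-level comparisons.** With 225 per arm and 80% power, the minimum detectable difference is 0.322 SD at R² = 0, 0.317 SD at 3% and 0.297 SD at 15%.

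**Supportive adjusted analysis of EPDS 13 or more.** I simulated 3000 trials per setting, with 225 per arm and 20% v 10%. Covariate R² is on the latent score.

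| Covariate R² | Chi-square power | Adjusted logistic power |
|---|---|---|
| 5% | 84.4% | 84.6% |
| 12% | 85.7% | 86.7% |
| 15% | 86.4% | 88.0% |
| 20% (r 0.45) | 86.1% | 88.7% |

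The gain is about 0-3 points. Chi-square power should not depend on the covariate, so its drift between rows is simulation error.

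**The case against.** The strongest objection is timing. As the recruitment text is ordered, women learn their arm before they answer the baseline questionnaire. T0 GAD-7 and PRAQ-R2 could then reflect pleasure or disappointment at the allocation. The screening EPDS, taken by telephone beforehand, is the one symptom score clearly placed before allocation, and every randomised woman has it. This stands, and it changes the remedy: the measures become sound covariates only if T0 is completed first.

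Second, the gain is assumed rather than documented, and at the low end it vanishes. This also stands. A reader might infer that GAD-7 keeps its full predictive strength because it is not an eligibility criterion. It does not, since selection on a correlated EPDS narrows it too.

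Third, a reader might infer that nothing but the truncated EPDS can enter these models. The plan does allow unbalanced baseline variables in, and its subgroup models bring in socioeconomic status, ethnicity and personality symptoms. That corrects the inference but does not close the gap. The imbalance rule chooses covariates after the data are seen, with no list or threshold, and imbalance is not what makes a covariate useful for precision.

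Fourth, a reader might take the carry-over of the ANCOVA to other outcomes to mean that GAD-7 is adjusted for EPDS instead of its own T0 value. That reading is strained. The natural sense is each outcome with its own baseline, and one clarifying sentence settles it. Most other secondary outcomes have individual entries naming only a postpartum time, so own-baseline adjustment helps few of them.

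**Conclusion.** The point holds as one of efficiency. The single covariate prespecified for the EPDS-score model can take four values and probably explains about 1-4% of outcome variance, given an unrestricted SD of 4-6 and a correlation of 0.4-0.6. Prespecifying measures already collected could recover some precision, but the size is modest and uncertain, from nothing to the 38 women per arm shown above. Every correlation behind that range is an assumption.

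A reader might go further and conclude that the ANCOVA is biased or the trial underpowered. The documents support neither: a weak covariate leaves the ANCOVA valid, the model is supplementary, and the primary test and its sample size do not use it.

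**What to change.** - Name T0 GAD-7 and PRAQ-R2, as continuous covariates together with EPDS, in the EPDS-score model.
- State that each other outcome is adjusted for its own T0 value where one exists (GAD-7, substance use).
- Optionally, add one supportive covariate-adjusted risk difference for EPDS 13 or more. The chi-square test stays primary.
- Have REDCap randomise and release the arm only once the T0 questionnaire is complete. Do not use as covariates any T0 values given after disclosure; for women enrolled that way, only the screening EPDS qualifies.
- State a rule for missing T0 values, so that no randomised woman leaves the adjusted model for that reason.

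The cost is a few sentences in the analysis plan and a small change in the order of enrolment steps. Women who do not complete T0 would then not be randomised. No new instrument is needed.

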Primary research question: Compared to a fully automated virtual (with a workbook or online material) intervention, what is the effect of the virtual intervention with telephone support for pregnant women with subclinical depressive symptoms on maternal depression at 3 months' postpartum? We adopted an indicated prevention strategy (targeted or secondary prevention), targeting women with symptoms of depression during pregnancy.

Secondary research questions: Compared to a fully automated virtual (with a workbook or online material) intervention, what is the effect of the virtual intervention with telephone support on: 1) maternal depression at 6 months' postpartum; 2) maternal anxiety, perceived stress, well-being, self-efficacy, self-compassion, sleep quality, tobacco, alcohol and drug usage, social functioning, social support, marital satisfaction, co-parenting and parental cognitions and practices, at 3 and 6 months' postpartum; 3) child's socioemotional development at ages 3 and 6 months; 4) maternal health care services utilization at 6 months' postpartum.

Tertiary research questions: What is the effect of a virtual intervention (with a workbook or online material) + telephone support on 1) partner depression, anxiety, perceived stress, well-being, self-efficacy, self-compassion, sleep quality, tobacco, alcohol and drug usage, social functioning, social support, marital satisfaction, co-parenting and parental cognitions and practices, at 3 and 6 months' postpartum; 2) What are the moderators of the effect (e.g., compliance to the intervention, COVID-19 infection of self or relatives, personality disorder traits, socioeconomic level, ethnicity, gender at the baseline, and sex of the child).

Method

[figure not shown]
Design

A randomized controlled trial (RCT) of 500 Quebec women with a 1:1 assignment to either virtual preventive intervention with telephone support or without telephone support (control). Figure 1 presents the trial design.

Population

French-speaking pregnant women older than 14 years old, with subclinical levels of depression (EPDS 9-12).

Figure 1. Trial design

Pregnant Women Recruitment

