Sample size. A meta-analysis of 58 studies indicates that the overall prevalence of postpartum depression is 17% (95% CI: 0.15–0.20) (53). This estimate falls within previously published estimates of 13%–19.2% (54, 55) and is similar to Hahn-Holbrook's 2018 finding of 17.7%. In-person interventions using the *Mother & Babies* course reported moderate effect sizes (OR = 0.28 (0.08-0.94) (22) and OR = 0.45 (0.19-1.10) (24)). Fully web-based without nurse-based telephone support reported small to moderate effect sizes (40). Given that the proposed intervention is offered virtually with nurse-based telephone support, we calculated a sample size that allows us to detect a moderate decrease in rates of clinical depression. We anticipate that 20% of pregnant women in the control group will have an EPDS score ≥ 13 at postpartum. A total of 500 pregnant women (250 per arm) is needed to detect an absolute reduction of 10% (i.e., 20% of women with EPDS ≥ 13 in the control arm versus 10% in the intervention arm) with 80% of power and a 2-tailed alpha of 5%. The sample size includes an attrition rate of 10% for 3 months' postpartum and another 10% between 3 and 6 months' postpartum. Based on our experience with pregnant women and the intervention (see Section about Pilot Study), the 10% attrition estimate is conservative. As most of the secondary

outcomes are continuous, the sample size provides enough power to detect small to moderate effect sizes using a 2-tailed alpha of 1% to account for multiple tests.

Compliance. We conducted a feasibility pilot study including 17 pregnant women. All began to read the online material and 2 refused further participation after 2 telephone calls, a dropout rate of 11.7%. We therefore expect that 80-90% of the intervention group will read at least some of the intervention material. Intervention compliance will be defined as completion of a minimum of 6/8 online modules and 6/10 telephone follow-ups. Compliance will be monitored automatically online and by nurses during telephone calls. Weekly text reminders will be sent out to maximize compliance (see details in Appendix H).

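### Secondary outcomes are judged at two-sided 0.01, but the plan reports them with 95% intervals, so a test and its interval can disagree

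*Combined protocol and SAP*

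**What the plan says.** Planned Analyses fixes two decision levels. For the primary outcome: "A two-sided significance level of 0.05 will be used for the primary outcome". For the rest: "a significance level of 0.01 (two-sided) will be used for secondary and other outcomes to account for multiple outcomes". The Sample size paragraph gives the same reason for the stricter level, stating that "the sample size provides enough power to detect small to moderate effect sizes using a 2-tailed alpha of 1% to account for multiple tests".

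The interval level is set separately:

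- **Binary secondary outcomes** (Planned Analyses): after naming chi-square tests, the plan adds "The corresponding 95% CI for the difference in proportions will also be provided".
- **EPDS scores** (Planned Analyses, the ANCOVA that supplements the chi-square comparisons): "With this model, we will obtain 95% confidence intervals of EPDS score differences between intervention arms at 3 and 6 months' postpartum".
- **Other continuous outcomes** (Planned Analyses): "For continuous variables, we will use ANCOVA models as described above". No interval level is stated here. The reference back leads to the EPDS model, whose only stated level is 95%.

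Nowhere does the plan mention 99% intervals, or say that the 95% intervals are unadjusted or descriptive.

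**The concern.** A 95% interval corresponds to a test at 0.05, and a 99% interval to a test at 0.01. Here the test uses one level and the interval the other. When p lies between 0.01 and 0.05, the report would call the outcome not significant and print beside it an interval that leaves out no difference.

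The plan does not say which of the two governs the conclusion. The emphasis could therefore be chosen after the results are known. A reader who relies on the intervals would be applying 0.05 to outcomes for which the sponsor deliberately chose 0.01. With many secondary outcomes, at least one such case is a realistic prospect.

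**Working it through.** **1. The plan's own power statement at 1%.** The Sample size paragraph gives 250 women per arm, 10% attrition by 3 months and another 10% by 6 months. Completers per arm are 250 × 0.9 = 225 at 3 months and 225 × 0.9 ≈ 202 at 6 months. The standardized difference detectable with 80% power at two-sided 0.01 is (2.576 + 0.842) × √(2/n):

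- n = 225: 3.418 × 0.0943 = 0.32
- n = 202: 3.418 × 0.0995 = 0.34

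This agrees with the plan's description of small to moderate effects. The 1% level is thus a working part of the design, not a stray remark.

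**2. Width.** The normal multipliers are 1.960 (95%) and 2.576 (99%). 1.960/2.576 = 0.761, so the planned intervals are about 24% narrower than those that match the test. 2.576/1.960 = 1.314, so matching intervals are about 31% wider.

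**3. Where the conflict lies.** For a continuous outcome in standard deviation units, ignoring any precision gained from the baseline covariate:

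| Completers per arm | Standard error | 95% half-width | 99% half-width |
|---|---|---|---|
| 225 | 0.0943 | 0.185 | 0.243 |
| 202 | 0.0995 | 0.195 | 0.256 |

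An observed difference of about 0.19 to 0.25 SD would be negative at 0.01 with a 95% interval that excludes zero. For proportions the match between chi-square test and interval is only approximate, because the two may use different variance estimates. The same band applies closely but not exactly.

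**4. Chance per outcome.** With no effect, P(0.01 < p < 0.05) = 0.05 − 0.01 = 0.04. With a true effect of the size detectable with 80% power at 0.01, the test statistic is centred on 3.418, and the chance is Φ(2.576 − 3.418) − Φ(1.960 − 3.418) = 0.200 − 0.072 = 0.13.

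**5. How many outcomes are affected.** The documents give no count, so two cases are shown.

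- *Narrow case, about 4* (assumption): only binary outcomes, taken as EPDS in the clinical range at 6 months, tobacco, alcohol and drugs.
- *Wide case, about 22* (this review's count): one score per scale, following the measurement times under Secondary outcomes, Parent and child assessments and Economic evaluation, and the secondary research questions where no time is given.
  - EPDS proportion at 6 months: 1
  - EPDS score at 3 and 6 months: 2
  - GAD-7 at 3 and 6 months: 2
  - Stress, well-being, self-efficacy, self-compassion and sleep: 5
  - Tobacco, alcohol and drugs: 3
  - Work adjustment, marital satisfaction, co-parenting and social support: 4
  - Parenting: 1
  - ASQ-3 at 3 and 6 months: 2
  - Infant temperament: 1
  - Service use: 1
  - Total: 1 + 2 + 2 + 5 + 3 + 4 + 1 + 2 + 1 + 1 = 22

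**6. Chance of at least one conflict when there is no effect.** Under independence this is 1 − 0.96^k.

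| Outcomes k | Expected conflicts (0.04 × k) | At least one, independent | At least one, correlation 0.5 |
|---|---|---|---|
| 4 | 0.16 | 1 − 0.96^4 = 15% | 14% |
| 22 | 0.88 | 1 − 0.96^22 = 59% | 42% |

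The last column assumes equicorrelated normal test statistics and averages over their shared component. The 0.5 is an assumption.

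**The case against.** The strongest reply is that a 95% interval beside a stricter test threshold is a legitimate way to report an estimate, and that it changes nothing about the test. The second half stands in full: the type I error of each secondary test remains 0.01 whatever interval is printed. The first half would stand if the plan labelled the intervals as unadjusted estimates. It does not.

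A second reply is that the mismatch is narrower than it looks. The explicit 95% sentence covers binary secondary outcomes, while the Sample size paragraph says that most secondary outcomes are continuous. For continuous outcomes, 95% is explicit only for EPDS scores, and the 3-month score comparison supplements the primary analysis at 0.05, so its interval is not clearly wrong. This is fair, and it is why the narrow case is shown. The cross-reference to the EPDS model still makes 95% the likelier reading for the other scales.

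A reader might go further and infer that the multiplicity protection fails: 0.01 equals 0.05/5, whereas the secondary research questions list far more than five outcomes ("maternal anxiety, perceived stress, well-being, self-efficacy, self-compassion, sleep quality, tobacco, alcohol and drug usage, social functioning, social support, marital satisfaction, co-parenting", among others). The documents do not support that. They promise no 5% familywise rate and name no family, number of tests or Bonferroni split, so there is no stated level to miss. Any total is the reviewer's and moves with the counting rule: about 22 by measurement schedule, 32 if every maternal and child outcome is tested at both time points, about 39 or 62 with partners added. The stricter level also helps. For 20 to 40 independent tests, the chance of at least one false positive is 1 − 0.99^20 = 18% to 1 − 0.99^40 = 33%, against 64% to 87% at 0.05. The 0.01 is best described as a stricter per-test level.

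**Conclusion.** The point holds as an inconsistency between decision rule and reporting. It is explicit for binary secondary outcomes and for the 6-month EPDS score, and probable for the other continuous outcomes. The chance that at least one outcome shows the conflict when there is no effect runs from about 15% (four outcomes, assumed, independent) to 42–59% (about 22 outcomes, this review's count, correlation 0.5 to independence). Real effects can add to this, with about a 13% chance per outcome at the effect size that has 80% power at 0.01.

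It does not show that the 0.01 level fails to deliver a stated protection, and it gives no ground for requiring a formal multiplicity procedure. The primary comparison at 0.05 and the 500 women are untouched. This is a cheap improvement, worth making before the data are seen.

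**What to change.** In Planned Analyses, replace the fixed 95% by a rule: 99% confidence intervals for every outcome tested at two-sided 0.01, including the EPDS comparisons at 6 months, and 95% for the primary 3-month comparison. State that the rule covers the other continuous outcomes too, so that the cross-reference leaves no doubt. Say which level applies to the supplementary 3-month EPDS score and use the matching interval.

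The cost is a sentence or two of text and one SAS option (ALPHA=0.01). Intervals become about 31% wider, for example 0.256 instead of 0.195 SD on either side of the estimate with 202 women per arm. The tests, their power and the sample size do not change.

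If the sponsor prefers to keep 95% intervals for comparison with other trials, the minimum is a sentence saying that they are unadjusted and that conclusions on these outcomes rest on the 0.01 test alone.
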